Endpoints	
Symptom Assessment:
 
A patient-reported outcome (PRO) instrument will be used to assess COVID-19-related symptoms (measuring signs and symptoms best known by the patient and measured from the patient perspective). The assessment will be performed every 24 hours at approximately the same time each day. The following symptoms will be included in the daily assessment (regardless of which symptoms the subject had at baseline, as new symptoms may appear following the baseline assessment):
 
 a. Stuffy or runny nose, sore throat, shortness of breath, cough, lack of energy or tiredness, muscle or body aches, headache, chills or shivering, feeling hot or feverish, nausea: subjects rate symptom at its worst over a 24-hour period using a 4-point scale for severity- 0=none, 1=mild, 2=moderate, 3=severe b. Vomiting, diarrhea: subjects rate symptom frequency over a 24-hour period using a 4-point scale for frequency- 0= not at all, 1=1–2 times, 2=3–4 times, 3=5 or more times c. Sense of taste, sense of smell (not included in the Primary Endpoint assessment): subjects rate symptom over a 24-hour period using a 3-point scale- 0= sense (of smell or taste) is the same as usual, 1= sense is less than usual, 2=have no sense 
Primary Efficacy Endpoint:
 
Time to Sustained Clinical Recovery defined as number of days from start of study treatment to Sustained Alleviation of Symptoms, evaluated from study day 1 onward. The endpoint will be considered to have been met at the earliest time point, starting on study day 1, at which the subject has reached Sustained Alleviation of Symptoms as defined by: (1) Blood oxygen saturation $\geq 94\%$ on room air at rest, (2) Oral temperature $< 38.0^{\circ}\text{C}$ AND (3) All COVID-19 associated symptoms (stuffy or runny nose, feeling hot or feverish, chills or shivering, cough, sore throat, lack of energy or tiredness, nausea, headache, muscle or body aches, shortness of breath, vomiting, diarrhea) (Symptoms related to smell or taste are not included in the primary endpoint) reported by the patient have reached a severity of “0 – none” or “1 – mild” in assessments for 4-point scale assessments and not known to have redeveloped any COVID-19 associated signs and symptoms (not including reduced sense of taste or smell) in a severity beyond mild for 4 consecutive days (inclusive of the day when clinical recovery was achieved) when assessed from the start of study treatment to day 28. To meet the primary endpoint, subjects must survive with no hospitalization to day 28.
 
Key Secondary Efficacy Endpoint:

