⁵ The study team will be reviewing the data reported by subject to ensure compliance, accuracy and completeness on days 1, 3, 5, 7, 9, 10, 14, 17, 21, 24, and 28. Beyond Study Day 10, once the subject meets the primary efficacy endpoint, the subject is not required to continue the self-assessment and reporting of COVID-19 symptoms. However, the study team, during the remote patient visits will evaluate and report the severity of COVID-19 associated symptoms as per the set frequency mentioned in the table.

⁶ Collect oximetry data once daily, with the caveat that if the daily O₂ saturation result is 90-93%, the subject will repeat the measurement 2 hours later. If the result is <90%, the subject is instructed to contact the study team. The study team will decide if a recheck in 2 hours is appropriate or the subject needs further medical evaluation. Oral temperature will be measured twice daily. Heart rate will be measured once daily.

⁷ Until the sub-study enrollment is completed, all subjects will be enrolled into the viral shedding sub-study. However, If they choose so, subjects can opt-out of participating in the viral shedding sub-study.

⁸ 1st shipment on day 5 (+1) for all samples collected and 2nd shipment on day 10 (+1) for all the remaining collected samples. Saliva samples of 2nd shipment can be handed-over to site staff during the in-person site visit on day 10 (Site staff to ship it to laboratory).

⁹ Activity to be performed at site with the help of site staff to ensure that the subjects are comfortable to perform at home by themselves from next day onwards.

¹⁰ Beyond Study Day 10, once the subject meets the primary efficacy endpoint, the subject is not required to continue the self-assessment and reporting of COVID-19 symptoms and vitals. However, the study team, during the remote patient visits will evaluate and report the severity of COVID-19 associated symptoms and vitals as per the set frequency mentioned in the table. Data will be entered into ePRO from Day 1 to Day 10 irrespective of whether sustained clinical recovery is met or not.

¹¹ Height and weight should be collected at the screening visit. In cases where the data was not collected at the screening visit, the date of collection will be recorded.

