To meet the primary endpoint, criteria 1 through 3 (above) should be met and the subject is not known to have redeveloped any COVID-19 associated signs and symptoms (not including reduced sense of taste or smell) at a severity beyond mild for 4 consecutive days (inclusive of the day when clinical recovery was achieved) assessed from the start of study treatment to day 28, and subjects must survive with no hospitalization to day 28. The time from start of study treatment to the earliest time point that one through three (above) are met will be considered for the primary efficacy endpoint. For example, if clinical recovery was reached on study day 5 and sustained over study days 6, 7, and 8, the time of reaching the endpoint will be study day 5.

The subject will assess and score the severity of each COVID-19 associated symptom on a 4-point scale (for all symptoms besides vomiting and diarrhea: 0= none, 1= mild, 2=moderate, 3=severe. For vomiting and diarrhea: 0 = not at all, 1 = 1-2 times, 2 = 3-4 times, 3 = 5 or more times). The patient's blood oxygen saturation and severity of COVID-19 associated symptoms will be evaluated and reported once daily, preferably at or around the same clock time, by the subject (for a period of 10 days or longer in case that the subject does not achieve the primary endpoint within the first 10 days).

Beyond Study Day 10, once the subject meets the primary efficacy endpoint, the subject is not required to continue the self-assessment and reporting of COVID-19 symptoms. However, the study team, during all the in-person and remote patient visits will evaluate and report the severity of each of the COVID-19 associated symptoms and vitals as per the set frequency mentioned in the *Schedule of Activities*, under study staff responsibility.

Subjects who develop new COVID-19 symptoms post-randomization will be counted towards the primary outcome. The definition of the primary endpoint for such subjects will be identical to the definition used for any other subjects. To have the endpoint, all symptoms (those existing at enrollment and those appearing post-enrollment, not including symptoms related to smell or taste) will have to be no worse than 1 - mild, regardless of whether they existed at randomization or not.

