- Proportion of subjects with COVID-19 progression, defined as the occurrence from study day 1 onward of any ED visit for COVID worsening or shortness of breath **OR** hospitalization for COVID worsening or shortness of breath **OR** death **OR** the development of symptomatic worsening from study day 1 onward (defined as ≥ 2 additional COVID symptoms at a level of moderate or severe which have not existed at baseline or fever (temperature of $\geq 38.0^{\circ}\text{C}$) which has not existed at baseline or oxygen desaturation (O₂ saturation $<94\%$) which has not existed at baseline) (broad progression).

Viral Shedding Sub-Study:

- Time (number of days) to negative conversion (defined as undetectable viral load) of detectable SARS-CoV-2 viral RNA in RT-PCR assays of saliva, from start of study treatment to date of last viral assessment. Included: all subjects with a positive PCR on study day 1 or 2 or 3. The endpoint will be evaluated from study day 1 onward.

Additional Secondary Efficacy Endpoints

- Time (number of days) to negative conversion of positive SARS-CoV-2 viral culture assays of saliva, from start of study treatment to date of last viral assessment. Subjects with a positive saliva SARS-CoV-2 PCR on any study day will have viral cultures performed. Subjects with a positive viral culture on study day 1 or 2 or 3 will be included in this analysis. The endpoint will be evaluated from study day 1 onward.

Exploratory Endpoints (details of the planned analyses are described in SAP 3.1):

- Proportion of subjects showing sustained clinical recovery by study Day 1, 3, 5, 7, 10, 14, 21.
- Proportion of subjects showing resolution of Symptoms by Days 1, 3, 5, 7, 10, 14, 21, where resolution is defined as symptom severity of 0 for all symptoms as well as temperature of $<38.0^{\circ}\text{C}$ as well as oxygen saturation of $\geq 94\%$.
- Proportion of patients showing negative conversion of detectable SARS-CoV-2 viral RNA in saliva on study day 1 or 2 or 3 to undetectable viral load on Study Days 3, 5, 7, and 10. Included: all subjects with a positive PCR on study day 1 or 2 or 3.
- Proportion of patients showing negative conversion of positive SARS-CoV-2 viral culture in saliva on Study Days 3, 5, 7 and 10. Subjects with a positive saliva SARS-CoV-2 PCR on any study day

will have viral cultures performed. Subjects with a positive viral culture on day 1 or 2 or 3 will be included in this analysis.

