9.2.4 Post Treatment Days (Day 14 to Day 28)

The following procedures will be performed at all follow-up visits (post-treatment days), expected to be done remotely, unless otherwise noted, on Day 14, 17, 21, 24, and 28:

- Assess for AEs
- Review and assess COVID-19 signs and symptoms
- Document all current medications, including medications over the counter and herbal medications
- Document subject's status as an outpatient, subsequently hospitalized, or died
- Perform clinical assessment and review reported vital signs (oral temperature, heart rate and oxygen saturation)
- The study team will be reviewing the data reported by subject to ensure compliance, accuracy and completeness on days 1, 3, 5, 7, 9, 10, 14, 17, 21, 24, and 28.
- Once the subject meets the primary efficacy endpoint, the subject is not required to continue the self-assessment and reporting of COVID-19 symptoms. However, the study team, during the remote patient visits will evaluate and report the severity of COVID-19 associated symptoms as per the set frequency mentioned in the *Schedule of Activities*, under study staff responsibility.

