10.6 Analysis of the Key Secondary Endpoint(s)

Proportion of subjects with COVID-19 progression will be presented with counts and percentage. Significance among group will be evaluated using Chi-square test or Fisher test as applicable. The corresponding confidence interval for the difference in proportions will be calculated.

Viral shedding sub-study (time in number of days to negative conversion of detectable SARS-CoV-2 viral RNA to undetectable viral RNA in RT-PCR assays of saliva, from start of study treatment to date of last viral assessment) will be analyzed using time-to event methods.

All secondary endpoint analyses will be performed for the mITT, mITT2 and PP populations.

Adjustment for multiple testing will be performed to control the overall type 1 error to no more than 5% for the interim and final analysis on the primary efficacy endpoint.

Moreover, for labeling purposes, a hierarchical approach will be used to control the overall type 1 error to $\leq 5\%$ for the primary and key secondary endpoints. The order of testing will be:

1. Clinical recovery
2. Broad progression (key secondary endpoint)
3. Narrow progression (key secondary endpoint)

Statistical significance cannot be claimed if the parameter on top of the parameter being tested did not reach statistical significance. For example, if clinical recovery was not statistically significant at final analysis, the other parameters will not be considered as having reached statistical significance (no matter the results obtained). If clinical recovery reaches statistical significance at final analysis and Broad progression (key secondary endpoint) does not, the remaining parameters will not be considered as having reached statistical significance and so on.

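### After Day 10, recovered subjects need only be assessed at five team visits while unrecovered subjects report daily, so detection of broad progression depends on recovery and may favour the arm that recovers faster.

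*Combined protocol and SAP*

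**What the plan says.** **Days 1-10.** Recording is the same for everyone. Footnote 10 of the Schedule of Activities (protocol section 2.3) says: "Data will be entered into ePRO from Day 1 to Day 10 irrespective of whether sustained clinical recovery is met or not".

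**After Day 10, endpoint met.** The same footnote says "the subject is not required to continue the self-assessment and reporting of COVID-19 symptoms and vitals". The study team then evaluates symptoms and vitals at the follow-up visits, which section 9.2.4 describes as "expected to be done remotely, unless otherwise noted, on Day 14, 17, 21, 24, and 28".

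**After Day 10, endpoint not met.** Section 4.0 has the subject report once daily "for a period of 10 days or longer in case that the subject does not achieve the primary endpoint within the first 10 days". The synopsis (study evaluations) follows symptoms and signs to Day 28. In the extracted Schedule table the marks for subject reporting stop at about Day 21, but that table may be broken.

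**Recall.** For most symptoms the synopsis says "subjects rate symptom at its worst over a 24-hour period using a 4-point scale for severity". No recall across the gap between visits is specified.

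**The endpoint.** Besides emergency department visits, hospitalization and death, broad progression includes "the development of symptomatic worsening from study day 1 onward", which covers two or more new moderate or severe symptoms, new fever, or new saturation below 94%. Section 10.6 compares it as a crude proportion by chi-square or Fisher test and places it second in the hierarchy, after clinical recovery. No rule in the supplied text equalises assessment days. Section 10.8.5 describes one sensitivity analysis, on relapse in the primary endpoint, and refers to SAP 3.1 for the rest.

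**The concern.** How often the diary-based components are observed after Day 10 is set by recovery, a post-randomisation outcome that treatment is meant to change. A one-day fever on Day 12 is recorded in a subject who is still reporting and can go unrecorded in one who has recovered. If the arms differ in the share still unrecovered after Day 10, the same true risk of late worsening yields different recorded proportions. Blinding and randomisation do not remove this.

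At stake is the first key secondary claim. It can be made only when the primary endpoint has succeeded, which is when a recovery difference between arms is most likely. Narrow progression is not affected in this way, because emergency visits, hospitalizations and deaths do not depend on the diary.

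**Working it through.** **1. The plan's own figure.** Section 10.2.2 plans 815 recoveries for 85% power at a hazard ratio of 1.25 (medians 5 v 4 days), with one interim look at 45% information and power-family spending (1.147).
- Interim alpha: 0.05 × 0.45^1.147 = 0.0200. Final nominal alpha by bivariate normal integration: 0.0369. Both match the plan.
- Power at 815 events: 84.8% if the futility bound is followed, 87.1% if it is ignored.

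The stated 85% is reproduced, so 5 v 4 days is used below as the design effect. The plan gives no rate, sample size or power for broad progression.

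**2. Required assessment days, Days 11-28.** Unrecovered: 28 − 10 = 18. Recovered: 5. If daily reporting ends at Day 21, the count over Days 11-21 is 11 v 3.

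**3. Share still unrecovered.** With exponential recovery, S(t) = 0.5^(t/median).
- Day 10: 0.5^(10/5) = 25.0% v 0.5^(10/4) = 17.7%.
- Day 14: 14.4% v 8.8%.

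**4. Mean assessed days.** Recovery on day r is confirmed at r+3. Daily reporting runs to the later of Day 10 and r+3, then visits only. Averaged over r, Days 11-28 hold 7.1 (placebo) v 6.4 (favipiravir) assessed days.

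**5. Daily-chance model.** Assumptions, none from the documents: each assessed day carries the same chance p of a qualifying reading, independently, in both arms and whatever the recovery status; a share e has already progressed by Day 10. With d assessed days:
- P(late) = average of 1 − (1 − p)^d
- P(broad) = e + (1 − e) × P(late)
- shift = difference / √[(P₁(1−P₁) + P₂(1−P₂))/625]
- two-sided error = Φ(−1.96 + shift) + Φ(−1.96 − shift)

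| p | e | Placebo | Favipiravir | Difference (points) | Two-sided error |
|---|---|---|---|---|---|
| 0.5% | 10% | 13.12% | 12.83% | 0.29 | 5.3% |
| 0.5% | 20% | 22.78% | 22.52% | 0.26 | 5.1% |
| 1% | 10% | 16.13% | 15.58% | 0.55 | 5.8% |
| 1% | 20% | 25.45% | 24.96% | 0.49 | 5.5% |
| 2% | 10% | 21.80% | 20.80% | 1.00 | 7.2% |
| 2% | 20% | 30.49% | 29.60% | 0.89 | 6.4% |

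Example (2%, 10%): standard error √[(0.2180×0.7820 + 0.2080×0.7920)/625] = 0.0232; shift 0.0100/0.0232 = 0.43; error 0.063 + 0.008 = 0.072. The 0.063 is the error in favipiravir's favour, against a nominal 0.025.

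**6. Daily reporting ends at Day 21.** Same model: 0.2-0.8 points, two-sided error 5.1-6.4%.

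**7. Episode model.** Late worsening comes as an episode with equal risk in both arms, unrelated to recovery, and is detected only if an assessment falls within it.
- On the five-visit schedule, episodes of 1, 2 and 3 days are caught for 5/18 = 28%, 10/18 = 56% and 15/18 = 83% of onset days. Episodes of 4 days or more are always caught.
- With late risk 5%, 10% or 20%, one-day episodes give 0.19, 0.37 or 0.75 points; three-day episodes give 0.05, 0.09 or 0.18.
- Two-sided error: 5.0-6.4%.

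**8. Longer medians.** With 9 v 7 or 13 v 10 days, the model of step 5 gives 0.4-1.7 points and 5.3-10.3%. The top value needs 13 v 10 days, p = 2% and e = 10%. If daily reporting ends at Day 21, the maximum is 7.4%.

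**9. Same assessment days for all.** In these models the artificial difference is 0 and the error returns to 5%, whatever the recovery effect.

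**The case against.** **The equal-chance assumption drives the size.** Recovered subjects have had four days without known symptoms beyond mild. If late fever or desaturation occurs mainly in unrecovered subjects, who report daily in both arms, little is missed and an arm difference largely reflects real recovery. At p = 2% an unrecovered subject has a 1 − 0.98^18 = 30% chance of a late event, which is high. Subjects still unrecovered after Day 10 may also have qualified already. All of this stands. It reduces the size without removing the mechanism.

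**Eighteen days is not certain.** The table may mean that daily reporting ends at Day 21. This stands, and both readings are shown above.

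**Some events may still be found.** Not requiring reports does not forbid them, so five days is a minimum. Adverse events are assessed at every visit, and section 9.3.2 names dyspnea and hypoxia. But no passage says that adverse events feed the endpoint.

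**Primary success does not guarantee the imbalance.** A reader might infer from the hierarchy that the bias is present whenever broad progression can be claimed. The documents do not support that. The Gehan Wilcoxon test weights early events (section 10.4), so it can succeed on a separation that has closed by Day 11. A late imbalance is then likely, not certain.

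**SAP 3.1** is cited but is not in the supplied text. If it already fixes the assessment days, the point falls.

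**Conclusion.** The point holds as a modest, avoidable weakness in a confirmatory secondary test. The unequal assessment after Day 10 is plain in the protocol. The direction favours favipiravir if fewer of its subjects remain unrecovered after Day 10; without such a difference there is no bias.

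Under 5 v 4 day medians and assumed daily chances of 0.5-2%, the artificial difference is about 0.2-1.0 points and the two-sided error about 5.1-7.2%, or 5.1-6.4% if daily reporting ends at Day 21. It is near nil if episodes last several days or late events occur mainly in unrecovered subjects. These rates apply to the broad-progression test at the 5% level once it is reached; the power to reach it is planned at 85%.

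A reader might take an error of about 10% as the expected size. That needs much longer medians and the highest assumed rate. Control medians of 3 to 15 days appear in section 10.2.2 as scenarios, but the definitive design uses 5 v 4.

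**What to change.** Before unblinding, state in the SAP that for the confirmatory broad-progression test:
- symptom, fever and desaturation components count from the daily records on Days 1-10;
- after Day 10 they count only from the study team's evaluations on Days 14, 17, 21, 24 and 28, in all subjects;
- emergency department visits, hospitalization and death count to Day 28 as now.

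Report the version using all diary data as a sensitivity analysis.

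The source must match as well as the days. Otherwise unrecovered subjects would be judged on self-report and recovered subjects on team evaluation. Section 9.2.4 lists a team assessment of symptoms at these visits for everyone, but vital signs are reviewed as reported. The SAP should therefore say which visit-day record is used.

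The cost is SAP wording, with no new data if the visit evaluations are recorded for all subjects. The downside is that between-visit diary events in unrecovered subjects are left out of the main test. The text should also state whether daily reporting by unrecovered subjects runs to Day 21 or Day 28.

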3.0 INTRODUCTION

3.1 Study Rationale

The ongoing COVID-19 pandemic is an urgent public health crisis with few if any rapid and practical solutions. The outbreak of COVID-19 has been declared to be a public health emergency of international concern by the World Health Organization (WHO), and the development of effective therapies for fast-spreading fatal COVID-19 is in an urgent need [1]. Given the seriousness and time-sensitive nature of this highly contagious virus, the medical and scientific communities must work quickly and efficiently to find a feasible way to address this global emergency.

COVID-19 begins as pure viral infection, involving viral replication and virulence. Once progressed, it evolves into a multifactorial disease with components of viral infection, hyper immune activation, and end organ damage and fibrosis. In fact, many of those with progressed COVID-19 do not shed virus anymore and their course can be improved by reducing their immune responses using dexamethasone. Thus, the suppression of viral replication, i.e. antiviral effect, is expected to be most impactful early during COVID-19, when no or mild symptoms are present.

Unlike remdesivir, which is available only as IV and is therefore mostly limited to patients with severe COVID-19 that require hospitalization, favipiravir is available in a tablet form and can be used also in outpatients with asymptomatic or mild infection [2]. Progression from mild to severe COVID-19 is more frequent among older persons and those with certain underlying comorbidities. [3]. As a result, such populations contribute unproportionally to death from COVID-19 [4]. The ability to mitigate COVID-19 symptoms has the potential to decrease progression to severe COVID-19 and is of great importance as it has the potential to save many lives. In addition, early effective treatment is expected to shorten and reduce viral shedding [5]. Viral shedding in patients with symptomatic COVID-19 typically continues for 4-15 days, and sometimes >15 days. During this period, patients are considered to be infectious. Shortening the duration of viral shedding may decrease the risk of progression to severe COVID-19 and diminish the period of infectivity, thus possibly decreasing the number of secondary cases. Two small studies from China demonstrated that favipiravir decreases the period of viral shedding in symptomatic patients with COVID-19 [6-7].

